Statistical Analysis Plan (SAP) for: VIA Family—a family-based early intervention versus treatment as usual for familial high-risk children.

ClinicalTrials.gov, NCT03497663,

SAP version 1. 25.05.2021

Roles and responsibility

[name] (ADM)

[name] (IG)

[name] (NT)

[name] (NH)

[name] (MN)

[name] (AT)

AT is primary investigator, ADM and NT wrote the SAP.

Background

Children of parents with mental illness (COPMI) have an increased lifetime risk for developing a mental illness themselves (Rasic et al. 2014). Already during childhood COPMI have an increased risk for experiencing pediatric psychopathology and they have lower levels of functioning in their everyday life compared to children without parental mental illness (Ellersgaard et al. 2018). Children who are born to and grow up with parents who experience a severe mental illness (SMI) have a twofold risk: an enhanced genetic and a psychosocial risk.

There is a need for early interventions and preventive strategies in order to help children with current their problems while also enhancing resilience in the families and thus, hopefully prevent the development of mental illness in the children later in life.

Objectives and Trial design:

The VIA Family study aims to investigate the effect of an early intervention for families with parental SMI on children's level of functioning and psychological wellbeing.

The trial is a randomized controlled trial in a two-armed parallel group design. The study aims to test for superiority of the VIA Family Intervention (VFI) compared to treatment as usual (TAU).

The participating families were randomly assigned to VFI or TAU. The allocation ratio was 1:1. Randomization was stratified by parental inclusion diagnosis. Randomization was performed through the randomization module within the electronic database REDCap (Harris et al. 2009).

For more information see study protocol (Müller et al. 2019)

Sample size

The power calculation of the sample size on the primary outcome of the study, the Children's Global Assessment Scale (CGAS), detected that the study needed to include 37 children in each group to show a high effect size of a change of 10 points on the CGAS, a scale from 1-100. For further details on sample size calculation see study protocol (Müller et al. 2019).

Trial population

All participants were screened for eligibility criteria before randomization.

[figure not shown]
Eligibility criteria were: Having (at least) one child between age 6-12. Living in the municipalities of Frederiksberg or Copenhagen (Denmark). The parent has been registered in the Danish registers as having been diagnosed with one of the following psychiatric diagnoses: Schizophrenia Spectrum Disorder, Bipolar Disorder, Recurrent severe or moderate depression, within child's life. Comorbid disorders were allowed.

Exclusion criteria were: Parent with insufficient Danish language skills to be able to engage in treatment. Having received intensive family treatment in primary sector within the last 26 weeks before study participation.

For more detailed information see study protocol (Müller et al. 2019).

See CONSORT flow-diagram for screening, inclusion process and follow-up (Fig. 1)

Fig. 1 CONSORT 2010 Flow Diagram

Withdrawal/Follow-up

Baseline characteristics of the study population will be presented in a descriptive table, presenting any possible differences between the two groups and the level of statistical significance.

Withdrawal from the study will be registered and reason for lost to follow up will be registered if possible. All participants who are missing at random will be included in the ITT analyses, see CONSORT diagram for drop out.

Statistical Analyses

Primary outcome

The primary outcome of the study is the change in CGAS. More precisely, the analysis will compare mean changes between baseline and 18 months in the CGAS to the VFI group.

The CGAS is a clinician rated scale from 1-100 (the higher the better) indicating the worst level of child's functioning within the last month. The CGAS will be used as a continuous outcome measure in the analysis.

The research question for the primary outcome is: Do children in the VFI group increase significantly more in CGAS at postintervention, when compared to the TAU group?

Primary Analysis: Intention-To-Treat

The primary analysis will be performed based on intention-to-treat (ITT) principles, meaning that the ITT population includes all randomized participants irrespective of their dropout status.

All outcome data will be analyzed collectively after the last participant has finished post intervention assessment. We will conduct an analysis of the primary outcome of the study followed by sensitivity analysis for the primary outcome. Further secondary analysis will be performed. See study protocol for an elaboration of primary and secondary outcomes (Müller et al, 2019).

The statistical analyses will be performed after follow-up data collection is completed. The statistical software R will be used for data analyses (Team 2010). Significance of results will be reported using two-tailed tests with a significance level of 5%. 95% confidence intervals will be reported for all estimates. The assumption that the data follows a normal distribution will be visually inspected using residual- and qq-plots, and if the data is not found to be normally distributed, log-scaling will be applied.

The primary outcome is the change in CGAS between 18-month follow-up and baseline. A linear mixed model will be used to model the data. Familiarity will be used as random nested factor in the analysis to accommodate for the non-independence that occurs between siblings that are part of the same family. Age, gender and variables with significant baseline differences between the groups will be used as covariates in the analysis. We report the mean difference in change between the VFI group and the TAU group effect and 95% confidence interval for this effect size.

Secondary Analyses:

Planned analyses for secondary outcomes: Change in mean scores on Child Behavior Checklist (CBCL), Teacher Report Form (TRF) and days of absence from school (\geq 15 %). Parent and family related outcome measures: Family Assessment Device (FAD) and Home Observation Measurement of the Environment (HOME).

Planned analyses for exploratory analysis: Change in mean scores on child related outcome measures: Child Affective Lability Scale (CALS), Behavior Rating Inventory of Executive Function (BRIEF) and Emotion Regulation Questionnaire (ERQ). Child Self-report on: self-esteem (This Is me), health-related quality of life (KIDSCREEN) and resiliency (Child and Youth Resilience Measure -CYRM). Parent and Family related outcomes: Parental Stress Scale (PSS) and Personal and Social Performance Scale (PSP).

For more information on secondary and exploratory outcome measures see study protocol (Müller et al. 2019).

Deviations from the intervention protocol will be handled in the sensitivity analysis. Adherences to intervention protocol have been pre-defined and are explained in detail in the study protocol (Müller et al. 2019)

There has not been planned any interim analysis before data collection has been finished at 18-months post intervention.

Missing Data

In the ITT analysis, assuming normality of the data and that data is "missing at random" (MAR), missing data will be handled through multiple imputations based on maximum likelihood inference of parameters and imputation of missing data from a linear regression model. The analysis will be based on 100 imputations and iterations until convergence. See table 1 for variables that will be included in the imputations.

Table 1: Variables for imputation on missing data. If not otherwise specified data from baseline and follow-up will be included

Child	Parent/family	Teacher	other
Clinician rated interview	Clinician rated interview	Surveys about the child	Group allocation (experimental/control)
CGAS score	PSP, Primary Caregiver, total score	TRF, total score	
KSADS, any diagnoses (binary: yes/no)	HOME, total score	BRIEF, total sore	
		SRS, total score (baseline)	
Cognitive tests	Surveys about the child		
RIST – total score	CBCL, total score		
TOMAL-II total score	BRIEF, total score		
RCFT - total score	SRS, total score (baseline)		
Self-report surveys:	Self-report surveys:		
KIDSCREEN, total score	PSS Primary Caregiver, total score		

Sensitivity Analysis

To validate results, the following sensitivity analyses will be performed after ITT analysis:

- 1. Impact of outliers (analyses without outliers)
- 2. Per protocol (analyses without protocol violations)
- 3. Attendance (analyses on participants with ≥50% attendance of intended personal meetings in treatment groups)
- 4. Adjusting for covariates (analyses without adjustments)
- 5. For outcome of school absenteeism, a different cut-off will be used for analysis.
- 6. CGAS change for one child per family (for families with multiple children in the study mean change from all children in one family will be used)

Results from the sensitivity analyses will only be reported if negative.

- Ellersgaard, D., K. Jessica Plessen, J. Richardt Jepsen, K. Soeborg Spang, N. Hemager, B. Klee Burton, C. Jerlang Christiani, M. Gregersen, A. Sondergaard, M. J. Uddin, G. Poulsen, A. Greve, D. Gantriis, O. Mors, M. Nordentoft, and A. A. Elgaard Thorup. 2018. 'Psychopathology in 7-year-old children with familial high risk of developing schizophrenia spectrum psychosis or bipolar disorder The Danish High Risk and Resilience Study VIA 7, a population-based cohort study', *World Psychiatry*, 17: 210-19.

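### Log-scaling, the only fallback for non-normal data, does not work on a change score that can be zero or negative, and it breaks with the mean difference in CGAS change that the SAP promises to report

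*SAP*

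**What the plan says.** The rule stands in the SAP under Primary Analysis: Intention-To-Treat. Normality is judged by eye: "The assumption that the data follows a normal distribution will be visually inspected using residual- and qq-plots". The remedy follows at once: "if the data is not found to be normally distributed, log-scaling will be applied". No other remedy for non-normality appears anywhere in the document. The analysis without outliers under Sensitivity Analysis is a robustness check and not a fallback.

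The next paragraph defines the variable to be modelled: "The primary outcome is the change in CGAS between 18-month follow-up and baseline". It is fitted with a linear mixed model, and the result is to be given as follows: "We report the mean difference in change between the VFI group and the TAU group effect", with a 95% confidence interval. Under Primary outcome the scale is fixed: "The CGAS is a clinician rated scale from 1-100". Under Sample size, 37 children per group are needed "to show a high effect size of a change of 10 points on the CGAS".

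**The concern.** The rule is not merely short on detail. As written it cannot be carried out on the variable that the SAP defines. A change between two 1-100 scores can be negative or zero, and a child who stays the same or gets worse has no log value. The SAP does not say whether a constant is added, which variable is logged, how the estimate is returned to points, or what in a plot counts as failure.

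If the fallback is triggered, the scale of the primary analysis, its effect measure and possibly its significance are chosen with the data in hand. The estimate may then not be readable against the 10-point target. A log also shortens only a right tail. With left-skewed changes it makes the skew worse.

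The same difficulty reaches the secondary and exploratory outcomes analysed as changes in mean score. School absence is listed among them but carries a cut-off; if it is analysed as a binary outcome, the log rule does not touch it.

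**Working it through.** **Inputs from the SAP.** Scale 1-100; outcome is change from baseline to 18 months; 37 children per group; target 10 points; two-sided 5%; 1:1 allocation; 100 imputations. **Not in the SAP:** the SD and the shape of the change distribution. These are assumed below and shown as ranges.

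**The plan's own figure.** The SAP gives neither SD nor power for its 37 per group. Solving the usual two-mean formula for the SD at a 10-point difference gives about 15.2-15.3 for 80% power, 13.1-13.3 for 90% and 11.8-11.9 for 95%. The figure can be neither confirmed nor refuted here, and the point does not depend on it. An SD range of 10-15 is used.

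**Step 1: can the log be taken?** The change runs from 1 − 100 = −99 to 100 − 1 = +99. The log is undefined for every value at or below 0. This needs no assumption beyond the stated scale.

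**Step 2: how many children could that be?** For normal changes the share is Φ(−mean/SD).

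| Assumed mean change | SD 10 | SD 13 | SD 15 |
|---|---|---|---|
| 0 | 50% | 50% | 50% |
| 5 | 31% | 35% | 37% |
| 10 | 16% | 22% | 25% |

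The fallback would be used when changes are not normal, so three other shapes were tried: right-skewed (gamma, shape 2), left-skewed (its mirror image) and heavy-tailed (t, 4 df). With TAU mean 0 or 3, VFI 10 points higher and SD 10-15, 30-59% of TAU and 1-29% of VFI children are at or below zero.

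**Step 3: reading with an offset.** Take TAU changes −10, −5, 0, 5, 10, with each VFI change 10 higher. The ratio of geometric means of (change + offset) reduces by cancellation. For offset 11 it is ((26 × 31)/(1 × 6))^(1/5) = 2.66. For offset 100 it is ((115 × 120)/(90 × 95))^(1/5) = 1.10. Offsets 20 and 50 give 1.56 and 1.20. The difference in points is 10 throughout.

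Significance depends on the offset too. The simulation used 37 per arm, TAU mean 0, VFI mean 10, 4000 runs, changes rounded and clipped at ±60, independent children, and a t-test on log(change + offset). Each cell gives SD 10/12/15.

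| Shape | Power, offset 1 − minimum | Power, offset 100 | Power, points | Offsets disagree |
|---|---|---|---|---|
| Left-skewed | 76/63/47% | 97/89/73% | 98/94/81% | 20.5/26.6/26.5% |
| Heavy-tailed | 86/76/62% | 98/93/83% | 99/95/85% | 12.1/17.7/21.4% |
| Right-skewed | 100/100/98% | 99/96/87% | 98/94/82% | 0.9/3.2/10.2% |

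For left-skewed changes, residual skewness goes from about −1.15 in points to between −1.5 and −4.4 after the log. For left-skewed and heavy-tailed changes, the prescribed remedy does worse than leaving the data alone.

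**Step 4: reading with raw scores.** Raw CGAS is at least 1, so the log exists, but the effect is a ratio. The same 10-point gain is 50/40 = 1.25 from a start of 40, 60/50 = 1.20 from 50, 80/70 = 1.14 from 70 and 90/80 = 1.125 from 80. This is not a mean difference in change.

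**Step 5: reading with undefined values dropped.** The SAP does not state this, and it would conflict with an ITT population of all randomised participants. It would remove the children counted in Step 2, which are those who did not improve, and more of them from TAU than from VFI.

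**The case against.** The strongest reply is that the rule says only that data are log-scaled. It stands in a general paragraph ahead of the model, and Table 1 imputes CGAS scores and not changes. Logging raw scores is then a plausible reading and is always computable. That stands as far as it goes: on this reading the undefined log disappears. The clash with the promised mean difference and with the 10-point target remains.

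The second reply concerns size. Setting the offset to 1 minus the smallest change sends the lowest child to log 1 = 0 and manufactures an outlier, so the pair of offsets above is close to a worst case. This is fair. With offsets 61 and 100, verdicts disagree in 3-12% of left-skewed, 2-7% of heavy-tailed and 0-2% of right-skewed trials. With 10 minus the smallest change against 100, the figures are 6-12%, 3-8% and 1-6%. With milder left skew (gamma, shape 16), the near-worst pair itself disagrees in 8-19%. The size shrinks, but the dependence on an unspecified constant does not go away.

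Third, the simulation has no family effect, covariates or imputation, and nothing in the SAP shows that changes will be skewed. Both are true. The figures illustrate the problem and do not predict this trial's result, and the chance that the fallback is used is unknown.

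Finally, deleting one sentence would be enough, and robust standard errors do not specifically correct skewness. That also stands. The added interval is a worthwhile check on the variance and clustering assumptions, and goes beyond the minimum repair.

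**Conclusion.** The concern holds. That the log is undefined for possible values of the primary outcome follows from the stated scale alone. That a log-scale effect is not the promised effect measure follows from the SAP's own text, whichever variable is logged. The SAP says mean difference in change without naming points, but the CGAS unit and the 10-point target settle the meaning.

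How much it could matter rests on assumed shapes and SDs of 10-15. Across the offset pairs tried, the choice of constant changes the significance verdict in anything from almost no trials to about 27% of them, most often when changes are left-skewed. The flaw is conditional on the fallback being triggered, so it should be fixed but does not by itself invalidate the primary analysis.

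**What to change.** Delete the log-scaling rule. State that the untransformed CGAS-point mixed model is primary whatever the plots show, and that the plots are descriptive only. Apply the same to the secondary and exploratory change scores.

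Alongside it, report for the same mean difference in points an interval with family-clustered, small-sample-corrected robust standard errors. It should be computed in each imputed data set ("The analysis will be based on 100 imputations and iterations until convergence") and pooled by Rubin's rules. Report it in all cases, so that no reading of a plot decides anything, and exempt it explicitly from the rule that "Results from the sensitivity analyses will only be reported if negative". If a family-level bootstrap is preferred, specify in advance how it is combined with the imputations.

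The cost is one SAP sentence replaced and a little extra analysis in R. The downside is some power if changes are truly right-skewed: at SD 15 the points model has 82% against 87-98% for a log with offset. In return, the effect measure stays the one the SAP promises.

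### Covariates for the primary CGAS model are chosen by baseline significance tests, so baseline CGAS usually, and the stratification factor almost always, stay out of the model

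*SAP*

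**What the plan says.** Under Primary Analysis: Intention-To-Treat, the SAP defines the endpoint as a change score: "The primary outcome is the change in CGAS between 18-month follow-up and baseline". On the model it says "A linear mixed model will be used to model the data", with family as a random factor to allow for siblings. The covariate rule follows: "Age, gender and variables with significant baseline differences between the groups will be used as covariates in the analysis". Age and gender are therefore fixed in advance, and everything else depends on a baseline test. No separate level is given for those tests, and the variables to be tested are not listed.

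The Withdrawal/Follow-up section confirms that these tests will be run: the baseline table is described as "presenting any possible differences between the two groups and the level of statistical significance".

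Under Objectives and Trial design the SAP states: "Randomization was stratified by parental inclusion diagnosis". No analysis section names that diagnosis as a model term. Baseline CGAS appears in the imputation list (Missing Data, Table 1) but is not named as a covariate.

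**The concern.** Whether a covariate is worth adjusting for depends on how well it predicts the outcome. Its baseline p-value does not measure that, because after randomisation any difference is chance. The rule therefore selects on the wrong criterion, with three consequences.

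- **Baseline CGAS.** It is likely to be the strongest predictor of CGAS at 18 months, yet it enters only if the arms happen to differ significantly on it. Otherwise the raw change score is analysed and regression to the mean is not corrected.
- **Parental inclusion diagnosis.** Stratification balances it, so it will almost never test as different. The rule drops the factor the trial randomised within, and the standard error is too large if diagnosis predicts the outcome.
- **Pre-specification.** The covariate set of the single confirmatory analysis is unknown until the baseline data have been tested, and the pool of candidates is open.

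**Working it through.** **Inputs from the SAP:** 37 children per group and a 10-point difference (Sample size); two-sided 5% level (Primary Analysis); 1:1 allocation of families (Objectives and Trial design).

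**Assumed, because the SAP does not give them:** raw CGAS SD of 15 at both visits; correlation r between baseline and 18 months of 0.3, 0.5 or 0.7; children treated as independent; 5% level for the baseline tests.

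**1. The plan's own figure.** The SAP refers to the protocol for the SD and power, so 37 cannot be derived from the SAP alone. With SD 15 and 80% power, 2 × (1.96 + 0.84)² × 15² / 10² gives 36 per group, and the exact t-test calculation gives 37. SD 13 with 90% power also gives 36 and 37. The figure is plausible and not in dispute; SD 15 is compatible with it.

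**2. Change score against baseline adjustment.** The SE of the treatment effect is SD × √(2(1−r)) × √(2/37) for the change score and SD × √(1−r²) × √(2/37) with baseline adjustment. The variance ratio is (1−r²) / (2(1−r)) = (1+r)/2. Power uses the normal approximation.

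| r | SE, change | SE, adjusted | Variance ratio | Power, change | Power, adjusted | n per arm for 80% power, change → adjusted |
|---|---|---|---|---|---|---|
| 0.3 | 4.13 | 3.33 | 0.65 | 67.8% | 85.2% | 50 → 33 |
| 0.5 | 3.49 | 3.02 | 0.75 | 81.8% | 91.2% | 36 → 27 |
| 0.7 | 2.70 | 2.49 | 0.85 | 95.9% | 98.0% | 22 → 19 |

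**3. The rule as written.** In 20,000 simulated null trials per r, baseline CGAS was selected in 4.8% to 5.2%. The SD of the estimate was 3.89/3.35/2.65 under the rule, against 3.32/3.04/2.51 with baseline always included, so the rule recovers little of the lost precision. In 6,000 trials per r with a true 10-point effect, power was 68/83/96% under the rule against 84/90/98%. Repeat runs gave 81% to 83% for the rule at r = 0.5.

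**4. Imbalance left uncorrected.** The SE of the baseline difference is 15 × √(2/37) = 3.49. Multiplied by t(0.975, 72 df) this is 6.95 points, the largest gap that stays non-significant. It shifts the change-score estimate by (1−r) × 6.95 = 4.9/3.5/2.1 points, in favour of the arm with the lower baseline. In near-miss trials (|t| above 1.5 but not significant, 8% to 9% of trials) the mean shift was 4.0/2.8/1.8 points, against about zero with adjustment. When the baseline p-value lies between 0.05 and 0.20 (about 15% of trials), coverage of the 95% interval falls to about 90/91/93%.

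**5. Open covariate set.** If k independent variables are tested, the chance that at least one enters is 1 − 0.95^k: 23% for k = 5, 40% for 10, 54% for 15 and 64% for 20.

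**6. Stratification factor.** With three equal strata, blocks of 4 and children randomised singly (all assumed), diagnosis tested significant at baseline in 0 of 5,000 simulated trials. If diagnosis explained 5% to 15% of the outcome variance (assumed), leaving it out would inflate the SE by 1/√(1−R²) = 1.026 to 1.085, that is 3% to 9%.

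**7. Other reading of the SD.** If 15 is the SD of the change score, power under the rule is about 81% at every r, and baseline adjustment raises it to about 94/90/87%.

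**The case against.** The strongest reply is that validity is not at stake. Averaged over randomisation, the estimate is unbiased. Simulated type I error under the rule was 3.9% to 4.5%, and overall interval coverage was 96.1/95.6/95.5%. The undercoverage in step 4 applies to a minority of trials and is offset where the baseline p-value exceeds 0.20 (coverage 97/96/96%). All of this stands.

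The sizes are also conditional. The SD and correlation are assumptions, the 6.95-point gap is the edge of non-significance and not an expected imbalance, and at r = 0.7 the power gain is only 2 points. Many candidate measures are probably correlated, so the percentages in step 5 are illustrative. The direction does not depend on these choices: (1+r)/2 is below 1 for every r below 1.

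The diagnosis part is the smaller one. On a change score, a diagnosis effect that is constant over time cancels, and the SAP shows no link between diagnosis and change. Any error is on the conservative side. Because families are randomised, unequal sibling numbers could leave some child-level imbalance, but a significant result remains unlikely.

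Sensitivity analysis 4 does not answer the concern. It only removes covariates and never adds baseline CGAS or diagnosis, and the SAP reports sensitivity results only when they are negative. A mixed model with baseline means constrained equal across arms would recover the precision, but the SAP does not specify one.

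**Conclusion.** The concern holds. The SAP states a rule that leaves baseline CGAS out of the primary model about 95% of the time, almost never admits the stratification factor, and leaves the rest of the covariate set to chance. With 37 per arm, a 10-point effect, SD 15 and independent children, the rule costs about 16 points of power at r = 0.3, 7 at r = 0.5 and 2 at r = 0.7. If SD 15 belongs to the change score, the cost is about 13, 9 and 6 points. The rule does not inflate type I error. It loses precision, leaves the estimate exposed to baseline imbalance just short of significance, and makes the confirmatory model data-dependent. The case rests mainly on baseline CGAS and pre-specification; omitting diagnosis adds a smaller, conservative loss.

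**What to change.** Replace the covariate rule with a fixed set, for example: *The model will include baseline CGAS, parental inclusion diagnosis (the stratification factor), age and gender as fixed effects, and family as a random intercept. No covariate will be chosen on the basis of baseline significance tests.* For each secondary outcome, use its own baseline value in place of baseline CGAS.

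The p-values in the baseline table then serve no purpose and are best removed, though that is a reporting matter once the covariates are fixed.

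The cost is SAP wording only. The variables are already held: baseline CGAS is in Table 1, diagnosis was needed for eligibility and stratification, and age and gender are already in the model. The added terms use about 3 degrees of freedom: 1 for baseline CGAS and 2 for the three diagnostic groups.

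### Imputing the primary outcome from a 29-variable list for a planned 74 children, without saying whether imputation parameters are redrawn, may make the primary interval under-cover or lose precision

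*SAP*

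**What the plan says.** The Missing Data section of the SAP assumes normality and data missing at random, and handles missing values in the intention-to-treat analysis by "multiple imputations based on maximum likelihood inference of parameters and imputation of missing data from a linear regression model". It adds "The analysis will be based on 100 imputations and iterations until convergence" and "See table 1 for variables that will be included in the imputations". Table 1 takes each measure at baseline and follow-up unless marked otherwise; only the two SRS scores are marked as baseline.

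The section does not say whether regression parameters are redrawn for each imputation, and it names neither a package nor a pooling rule.

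On size, the Sample size section says "the study needed to include 37 children in each group" to show "a change of 10 points on the CGAS". The primary model, described under Statistical Analyses, adjusts for age and gender and has a random family factor. None of these three is in Table 1, nor is the parental diagnosis used to stratify randomization.

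**The concern.** The primary result is the multiply imputed intention-to-treat comparison of CGAS change, so the imputation step helps set the width of the headline confidence interval. A regression with nearly thirty coefficients, fitted on some fifty to seventy children, is sensitive to how parameter uncertainty is treated.

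- **Parameters held at their maximum likelihood values.** The residual variance is underestimated and uncertainty in the coefficients is left out. Imputed values vary too little between imputations, and the interval is too short. That error favours false positive findings.
- **Parameters redrawn.** That uncertainty is carried through and coverage is protected, but the long predictor list adds noise to every imputed value and costs precision in a small trial.

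A hundred imputations help with neither. They bring the factor 1 + 1/m in Rubin's variance down to 1.01, which controls simulation noise only.

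**Working it through.** **1. Size of the trial.** The SAP gives 37 per group, so 2 × 37 = 74. It leaves SD and power elsewhere ("For further details on sample size calculation see study protocol"), so 37 cannot be strictly reproduced. It is plausible: n per group = 2(z₀.₉₇₅ + z_power)² SD²/Δ². With Δ = 10, SD 15 and 80% power this is 2 × (1.960 + 0.842)² × 225/100 = 35.3, rounded up to 36; a t-test with 37 per group has 80.8% power. SD 15 is therefore a reasonable scale for what follows.

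**2. Variables in Table 1.** Child: CGAS, KSADS, RIST, TOMAL-II, RCFT, KIDSCREEN (6). Parent/family: PSP, HOME, CBCL, BRIEF, PSS (5). Teacher: TRF, BRIEF (2). That is 13 measures × 2 visits = 26, plus 2 baseline SRS scores, plus group = 29.
- Predictors of a missing 18-month CGAS: at most 28.
- For a child lost to all follow-up: 13 + 2 baseline scores + group = 16.

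**3. Residual variance at its ML value.** With n children observed and k coefficients including the intercept, its expectation is (n − k)/n of the true value.

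| Missing | n observed | k = 29 | k = 17 |
|---|---|---|---|
| 10% | 67 | 38/67 = 0.57 | 50/67 = 0.75 |
| 20% | 59 | 30/59 = 0.51 | 42/59 = 0.71 |
| 30% | 52 | 23/52 = 0.44 | 35/52 = 0.67 |

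**4. Effect on the primary interval (simulation).** Assumptions: 74 independent children, SD 15, baseline to follow-up correlation 0.5, correlation 0.3 among baseline variables, values missing completely at random, no true effect, change regressed on group, age and gender, 100 imputations, Rubin's rules with small-sample degrees of freedom, 1,500 runs per cell. The short model uses baseline CGAS and group only. Entries are coverage of the 95% interval, with mean width in CGAS points in brackets.

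| Missing | Fixed ML, 28 | Redrawn, 28 | Fixed ML, 16 | Redrawn, 16 | Redrawn, short |
|---|---|---|---|---|---|
| 5% | 94.9% (14.17) | 95.8% (14.67) | 95.7% (14.33) | 96.5% (14.68) | 94.4% (14.41) |
| 10% | 94.8% (14.42) | 96.8% (15.53) | 94.7% (14.53) | 95.4% (15.28) | 95.1% (14.73) |
| 20% | 93.1% (14.83) | 96.9% (17.53) | 93.4% (14.86) | 96.5% (16.74) | 94.3% (15.60) |
| 30% | 90.8% (15.41) | 97.1% (20.57) | 92.6% (15.35) | 97.3% (18.86) | 96.3% (16.59) |

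Monte Carlo error is √(0.95 × 0.05/1500) = 0.6 percentage points, and a little more at lower coverage.

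Width of redrawn 28 over redrawn short:
- 5%: 14.67/14.41 = 1.02
- 10%: 15.53/14.73 = 1.05
- 20%: 17.53/15.60 = 1.12
- 30%: 20.57/16.59 = 1.24

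With 16 predictors the ratios are 1.02, 1.04, 1.07 and 1.14.

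**5. Second simulation, also with 74 children, using a six-auxiliary model as the short list.** At 10/20/30% missing, fixed ML covered 93.6/92.0/89.8% with the full list and 93.9/94.1/92.6% when only baseline data and group were usable. Redrawn parameters gave 95.7-97.3% coverage and intervals about 8/16/28% wider than the six-auxiliary model. The ranges in the conclusion span the two simulations.

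**The case against.** - **The text does not say that parameters are fixed.** Maximum likelihood or EM estimates refitted on bootstrap samples fit the same words and are proper. This stands: the SAP leaves a step unstated and does not prescribe an improper method.
- **A valid but wide interval is inefficient, not wrong.** This stands. The two readings have different consequences and should not be merged into one error.
- **The missing rate and the enrolled number are not visible.** The 74 is the planned requirement, and dropout is in a figure that is not shown. This stands. At 5% missing the first simulation finds no real loss under either reading; at 10% the loss is small.
- **28 predictors is the upper limit.** It applies only where CGAS is missing but the other follow-up measures were observed. This stands, and the 16-predictor columns give the generally milder case.
- **Part of the under-coverage comes from the ML variance estimate.** With fixed coefficients but an unbiased residual variance, the first simulation gives 94.7% at 20% missing and 93.2% at 30% with 28 predictors. This stands, although the SAP's wording does not point to that correction.
- **A pre-specified list of total scores is defensible, and follow-up teacher and parent scores may be the best information when only the clinician's interview is missing.** This stands in part. It argues against dropping all follow-up auxiliaries, not against choosing a shorter list.
- **The absence of age, gender and family from Table 1 is a separate mismatch.** This is fair. The simulations ignore family clustering and do not measure that mismatch, so it adds nothing to the figures above. It belongs in the same edit.

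A reader might infer that the primary interval is bound to be wrong. The SAP does not support that: it shows no missing rate, and its wording allows a proper method.

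**Conclusion.** The point holds as a conditional weakness in how the primary analysis is fixed.

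- **Parameters held at ML values:** coverage of the 95% interval is roughly 94-95% at 10% missing, 92-93% at 20% and 90-91% at 30%. With 16 predictors it is about 93-94% at 20% and 93% at 30%.
- **Parameters redrawn:** coverage is at or above nominal, but the interval is about 5-8%, 12-16% and 24-28% wider than with a short list, and less so with 16 predictors. At 20% missing the first simulation's ratio corresponds to (15.60/17.53)² = 0.79, or about a fifth of the information.

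These figures assume 74 independent children and the stated range of missing rates. The first simulation also has data missing completely at random and the correlations listed. The penalty would differ if the auxiliaries predicted CGAS more strongly than assumed.

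This is more than absent detail. Beyond low missing rates, the listed variables combined with the ML wording give a worse interval than a readily available alternative under either reading.

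**What to change.** Amend the Missing Data section and Table 1 as follows.

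1. State that imputation parameters are redrawn for each imputation, by Bayesian regression draws or bootstrap-EM, and that results are pooled by Rubin's rules.
2. Add to the imputation model the analysis variables that Table 1 omits (age, gender, family) and the parental diagnosis stratum.
3. Either cut the auxiliaries to a short, pre-named set, which may include follow-up scores, or keep the full list with a stated ridge prior.

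The cost is a few lines of SAP text and a change to the imputation code. A shorter list gives slightly less auxiliary support for the missing-at-random assumption; a ridge prior brings slight shrinkage. Step 1 alone removes the risk of under-coverage from fixed parameters, and step 3 recovers precision.
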